9.2 Recruitment Phase

The study team will be sent a full list of results each week from the laboratory and they will then contact women with their results. Women who are seropositive (have previously had infection) will be sent a letter with this result and be invited to take part in the cCHIPS study alongside information about the study. The GP will also be informed about women who are seropositive using appropriate letters. A very small minority of women may be found to have recent infection and as receiving these results may generate anxiety in the women and their families these will be communicated by a clinical member of the team by phone. A letter may subsequently be sent outlining what was said for reference. This group of women will be referred to the Fetal Medicine Unit (FMU) for further investigation and counselling. To expedite this process all such results will be discussed with [name] (or a designated specialist in her absence) to arrange a timely clinic appointment at the FMU. A letter will also be sent to the GP to inform them of the result and the referral to FMU.

Contact will be made with the potential participant screened via telephone, email, post and/or face-to-face. Eligibility criteria will be checked at this point. If the initial contact with the potential participant is face to face, informed consent can be sought at this point followed by the study procedures related to Visit 1. If the initial contact between the study team and potential participant is not face to face, a face to face appointment either at the participant's home or at a clinical setting will be arranged for the informed consent. The participant will be asked to sign an informed consent form for participation in the study and a unique identification number will be assigned to the participant.

As part of the eligibility inclusion criteria, all participants must provide written consent to the self-sampling of saliva, urine and vaginal secretions to enable them to participate in the study. Written informed consent will also be sought for the study team to collect a venous blood sample from the participants at each study visit, however if consent is not given to this the participant can still take part. Similarly, informed consent will be sought for leftover study samples to be stored and used in future ethically approved research in CMV infection but if consent is not given to this the participant can still take part.

9.3 Study Visit Phase

There will be four study visits (Visit 1, Visit 2, Visit 3, and Visit 4) for each participant:

- Visit 1: as soon as possible following screening, aiming up to 16 weeks and 6 days gestational age (early in pregnancy)
- Visit 2: 20 gestational weeks or any time in 2nd trimester from 17 weeks and 0 days gestational age to 26 weeks and 6 days gestational age (mid pregnancy)

- Visit 3: 28 gestational weeks or any time in 3rd trimester from 27 weeks and 0 days gestational age onwards (late in pregnancy)
- Visit 4: from the time of birth to 1 week postnatal age (postpartum period)

The timing for each visit was chosen following a discussion with the obstetric member of the trial management team ([name]) and our PPI group (the South London Maternal and Paediatric Infection & Immunity Patient and Public Involvement group) to strike a balance of coinciding with routine antenatal appointments for the convenience of the participants to promote on-going participation, and capturing samples throughout pregnancy at varying gestational stages. Where a visit is not possible to coincide with routine antenatal (or postnatal) appointments (in particular Visit 1), this will then take place in a clinical setting, and if still not possible, in the participant's home.

9.3.1 Visit 1

At Visit 1, after the participant has signed the written informed consent, the relevant study procedures can be performed in any order, which are:

- Background questionnaire
- Contact questionnaire
- Self-sampling of saliva, urine and vaginal secretions
- Venous blood sampling where consent is obtained

10.3.1.1 Questionnaires

The participant will be asked to complete two questionnaires:

- Background questionnaire: This will collect information on sociodemographic details such as ethnicity, age, living arrangements, number of children, occupation, age of child(ren), as well as existing medical conditions, previous child(ren) with cCMV and their awareness of CMV.
- Contact questionnaire: This will collect information on the participant's amount of handling and contact with child(ren)'s urine and saliva over the preceding two weeks. This will be collected at each visit.

Both questionnaires will be completed electronically on an electronic device (and if not possible on a paper copy) and will be completed during Visit 1.

10.3.1.2 Self-sampling of Saliva, Urine and Vaginal Secretions

At the Visit 1, the study team will explain and provide the participant with the ethically approved, study specific, written instructions on how to perform self-sampling of saliva, urine and vaginal secretions. The study team will collect these samples on the same day of the sampling. Self-sampling of saliva, urine and vaginal secretions will be performed on the day of each visit by the participant, using the written instruction provided without the need for any supervision by the study team, however the participant will be encouraged to seek advice and ask the study team any questions they may have regarding the self-sampling techniques. The participant will be provided with enough self-sampling kits to last them for the whole study period.

10.3.1.3 Venous Blood Sampling

Where consent is obtained, a venous sample will be collected at Visit 1, and at every visit. Any person that has received the appropriate training to perform venepuncture can collect the study blood samples. The participant's antenatal (or postnatal) clinical care team can also collect the study blood samples, for example, the participant may be due for a routine blood sampling as part of her antenatal (or postnatal) care and therefore the additional venous blood sample could be collected by her obstetrician or midwife at the same time for the study. However a member of the study team must perform any processing, packaging and transporting of the study sample to the laboratory.

9.3.2 Visit 2

Pregnant women booked for their antenatal care in St George's Hospital will attend a routine antenatal appointment at 20 gestational weeks. This is the timing chosen for Visit 2. Participants will be asked to inform the study team when their 20 gestational week antenatal appointment will be, and if any changes to the appointment date, the participant will be asked to make contact with the study team to inform them. If this timing is not suitable, the Visit 2 can be performed at a different time within the participant's second trimester from 17 weeks and 0 days gestational age to 26 weeks and 6 days gestational age.

At Visit 2, the relevant study procedures are:

- Contact questionnaire
- Self-sampling of saliva, urine and vaginal secretions
- Venous blood sampling where consent is obtained

The study team will send the participant a text reminder a day in advance of the Visit 2 to:

- Remind them of the visit
- Remind them to perform the self-sampling of saliva, urine and vaginal secretions on the date of the Visit 2 and to bring it with them to Visit 2
- Inform them that an email has been sent to them with a link to complete the contact questionnaire for Visit 2.

Although a face-to-face contact with the participant may not be necessary, a member of the study team will need to be available on the day of Visit 2 to:

- Collect the self-samples from the participant (or the participant can leave them with their direct antenatal team if the Visit 2 is coincided with their 20 gestational week routine antenatal appointment and the study team can collect it from the direct antenatal team)
- Perform venepuncture to collect a venous blood sample (or to collect the venous blood sample already taken in the event that the venepuncture and blood sampling is performed by the participant's direct antenatal team)
- If the participant does not have access to an email address, a paper copy of the contact questionnaire can be posted to the participant's home address.

9.3.3 Visit 3

- Pregnant women booked for their antenatal care in St George's Hospital will attend a routine antenatal appointment at 28 gestational weeks, which also includes a routine antenatal blood test. This is the timing chosen for Visit 3. Participants will be asked to inform the study team when their 28 gestational week antenatal appointment will be, and if any changes to the appointment date, the participant will be asked to make contact with the study team to inform them. If this timing is not suitable, Visit 3 can be performed at a different time within the participant's third trimester from 27 weeks and 0 days gestational age onwards.

At Visit 3, the relevant study procedures are the same as Visit 2, which are:

- Contact questionnaire
- Self-sampling of saliva, urine and vaginal secretions
- Venous blood sampling where consent is obtained

Just like Visit 2, the study team will send the participant a text reminder a day in advance of Visit 3 to:

- Remind them of the visit
- Remind them to perform the self-sampling of saliva, urine and vaginal secretions on the date of the Visit 3 and to bring it with them to Visit 3
- Inform them that an email has been sent to them with a link to complete the contact questionnaire for Visit 3.

Just like Visit 2 where a face-to-face contact with the participant may not be necessary, a member of the study team will need to be available on the day of the participant's Visit 3 to:

- Collect the self-samples from the participant (or the participant can leave them with their direct antenatal team if the Visit 3 coincided with their 28 gestational week routine antenatal appointment and the study team can collect it from the direct antenatal team)
- Perform venepuncture to collect venous blood sample (or to collect the venous blood sample already taken in the event that the venepuncture and blood sampling is performed by the participant's direct antenatal team)
- If the participant does not have access to an email address, a paper copy of the contact questionnaire can be posted to the participant's home address.

9.3.4 Visit 4

The participant will be reminded to let the study team know when they are in labour/have delivered. A reminder text will also be sent to all participants at 37 gestational weeks to remind them to let the study team know when they are in labour/have delivered. Effort will be made to perform Visit 4 when the participant is still on the postnatal ward provided this also suits the participant. If this timing is not suitable, Visit 4 can be performed at a different time within the first postnatal week, either at home or at a clinical setting, provided the participant is happy to bring her newborn with her to perform the newborn saliva sample. A face-to-face contact with the participant will be necessary to collect the saliva sample from the newborn for cCMV screening.

In the event that the participant delivers prematurely, provided the participant is still happy to remain in the study and the investigator has no concern with the participant remaining in the study, the specified visit number for this will be the subsequent visit of the previous visit and no further visits will be required (for example if the participant delivers her newborn at 32 weeks and the last visit she had was Visit 2, this will be Visit 3 labelled study visit equivalent to Visit 4).

Study Procedures	Screening	Visit 1	Visit 2	Visit 3	Visit 4
Eligibility criteria	X				
Informed consent		X			
Background questionnaire		X			
Contact questionnaire		X	X	X	X
Self-sampling of saliva, urine & vaginal secretions		X	X	X	X
Venous blood sampling*		X	X	X	X
Feedback questionnaire					X
Salivary swab of newborn*					X

At Visit 4, the relevant study procedures are:

- Self-sampling of saliva, urine and vaginal secretions
- Venous blood sampling where consent is obtained
- Screening newborn for cCMV
- Contact questionnaire
- Feedback questionnaire

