10.3.4.2. Screening Newborn for cCMV

Although the vertical transmission rate for non-primary maternal CMV infection (as all participants are CMV seropositive) is very low at around 2% [Liesnard 2000; Revello 2002], all participants entering into the cCHIPS study will be offered the opportunity for their newborn to have cCMV screening where a saliva swab of the newborn will be collected by the study team. This will be done within the first week of the newborn's life, to ensure that if the newborn was diagnosed with cCMV and meets the criteria for treatment, this can be done in a timely way, as the current guidelines recommend treatment to begin within the first month of life. The decision to offer to screen the participants' newborns for cCMV was made following a discussion with our PPI group.

A positive CMV salivary swab result will be communicated to the participants by phone by a clinically qualified member of the research team and arrangements will be made for appropriate clinical follow up. This will involve referral to the paediatric infectious diseases team, according to established clinical pathways. Responsibility for the clinical care of the newborn, whether established as having cCMV infection or not, will remain with the clinical team

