9.4 Summary flow chart of study assessment

*If consent obtained

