10.6.5. Sample collection and sample storage due to disruption caused by COVID-19 Pandemic

During the COVID-19 outbreak, face-to-face study visits, new recruitment and screening are suspended. Remaining participants will be offered the opportunity to continue with their study participation through the storing of their samples according to their usual study visit time-points at home until it is safe for the study team to collect the samples from the participants. This will involve the participants continuing to perform self-sampling of saliva, urine and vaginal secretions but instead of providing the samples to the research team on the day of the sampling, they will place the samples inside a securely sealed bag and store the sealed bag in the freezer at home. Participants will be provided with written instructions on how to do this and any additional sampling consumables via post. During this period of time it will not be possible to take blood samples or saliva swabs of newborns and so these will be seen as missing data points. For participants who do not agree to the storage of their samples in the freezer, or who lack access to a freezer, they will be withdrawn from the study or resume their study visits normally when it is safe to do so if suitable. Collection of home frozen samples will take place once the situation

has improved and we are able to see participants face-to-face. Participants will be contacted to update them on the changes required to the study due to the COVID-19 outbreak.

10 Safety Events

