13.4.3 Secondary endpoint analysis

For each sample type (saliva, urine, vaginal secretions), the percentage of participating women with detectable CMV DNA as measured by quantitative PCR, will be calculated for each study visit (Visit 1, Visit 2, Visit 3, Visit 4), and cumulatively, with 95% CIs.

For each study visit (Visit 1, Visit 2, Visit 3, Visit 4), the percentage of participating women with detectable CMV DNA as measured by PCR, will be calculated for each sample type (saliva, urine, vaginal secretions), and cumulatively, with 95% CIs

CMV shedding will also be assessed quantitatively, as measured by quantitative PCR on the amount of CMV DNA detected, in each sample type and at each study visit, separately and cumulatively, with 95% CIs.

The distributions of sample type, study visit number, detectable shedding and quantity of shedding will be summarised graphically and described using means and medians, as appropriate.

Factors associated with CMV shedding as a binary outcome (detectable shedding versus no detectable shedding) will be investigated using multivariable mixed effects models. Potential risk factors will be those assessed using the study sociodemographic questionnaire at Visit 1 and risk factor questionnaires at all visits (these variables may be time-varying) – these will include ethnicity, age, number of children, parental occupation, age of child(ren), and type of handling with child(ren)'s urine and saliva.

Acceptability of the study design and procedures will be analysed descriptively, for example by calculating mean scores derived from satisfaction scales. We will also investigate factors associated with satisfaction, defined as a binary variable, using logistic regression. We will summarise free text comments made through the feedback questionnaire.

The percentage of eligible women who consent to participate, and the percentage of participants who complete the study (provide urine, saliva and vaginal secretion samples and questionnaire data at all four study visits, with or without blood and newborn saliva samples), will be calculated.

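### A Visit 4 held off the postnatal ward depends on bringing the newborn for an optional swab, so some women could lose their own postpartum samples and completer status

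*Combined protocol and SAP*

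**What the plan says.** Section 9.3.4 (Visit 4) sets out two settings for the postpartum visit.

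- **On the ward, the default.** "Effort will be made to perform Visit 4 when the participant is still on the postnatal ward provided this also suits the participant". No newborn condition is attached.
- **Off the ward.** If the ward timing does not suit, "Visit 4 can be performed at a different time within the first postnatal week, either at home or at a clinical setting", but this is qualified: "provided the participant is happy to bring her newborn with her to perform the newborn saliva sample". The next sentence explains that the swab needs face-to-face contact.

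Other sections treat the swab as optional.

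- Section 10.3.4.2 (Screening Newborn for cCMV): "all participants entering into the cCHIPS study will be offered the opportunity for their newborn to have cCMV screening".
- The assessment table marks the newborn swab with an asterisk, which the footnote in section 9.4 explains as "If consent obtained". Venous blood carries the same asterisk.
- Section 13.4.3 (Secondary endpoint analysis) defines a completer as a woman who gives urine, saliva, vaginal samples and questionnaire data "at all four study visits, with or without blood and newborn saliva samples".
- Section 10.6.5, on the COVID-19 disruption, keeps maternal self-sampling going at home and says of the rest that "it will not be possible to take blood samples or saliva swabs of newborns and so these will be seen as missing data points".

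**The concern.** The swab may be declined, yet the off-ward sentence makes accepting it a condition of the visit. No other optional procedure works this way. Blood is also optional, and no visit depends on it.

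The mother's own samples do not need the baby. Section 10.3.1.2 has her self-sample without supervision, using kits supplied for the whole study.

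Two secondary results are exposed: the Visit 4 shedding percentages by sample type, and the proportion of participants completing the study. Completion matters in a study whose stated aim is to judge the feasibility of larger ones. A woman counted as a non-completer because of a swab she was free to refuse would make the maternal schedule look harder to complete than it is.

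**Working it through.** The plan gives no figure for Visit 4 setting, swab uptake or expected completion, so there is nothing to reproduce. The check is first textual and then an illustration of size.

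**Step 1. Follow each type of woman through the text.**

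| Visit 4 setting | Newborn brought for swab? | Maternal Visit 4 samples under 9.3.4 | Can be a completer under 13.4.3? |
|---|---|---|---|
| Ward | Yes | Yes | Yes |
| Ward | Swab declined | Yes (no condition attached) | Yes |
| Home or clinic | Yes | Yes | Yes |
| Home or clinic | No | No route stated | No, because the Visit 4 samples are missing |

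Only the last row is a problem. There the loss comes from the visit not being held; the missing swab itself does not count against completion.

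**Step 2. Check which endpoints are touched.** Sections 14.2.1 and 13.4.2 restrict the primary endpoint to samples taken during pregnancy. Visit 4 is postpartum and cannot affect it. The Visit 4 percentages and the completion proportion in section 13.4.3 can be affected.

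**Step 3. Illustrate the size.** Inputs:

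- N = 200, the target in section 13.3.1, taking all 200 to reach Visit 4 (a simplification)
- a = share of Visit 4s not held on the ward, assumed 25-75%
- b = share of those women who do not bring the newborn for the swab, assumed 5-20%

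Women affected = N × a × b.

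- Low: 200 × 0.25 × 0.05 = 2.5 women (1.25%)
- Middle: 200 × 0.50 × 0.10 = 10 women (5%)
- High: 200 × 0.75 × 0.20 = 30 women (15%)

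These percentages equal points of completion only if every affected woman would otherwise have completed all four visits, so they are upper values for the given inputs.

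**Step 4. Compare with sampling error.** If completion were 80% (assumed), the 95% half-width at n = 200 is 1.96 × √(0.8 × 0.2 / 200) = 0.055, or 5.5 points. The low and middle cases (1.25 and 5 points) lie below this, and the high case (15 points) lies above it.

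**Step 5. Precision at Visit 4.** With 30 women lost, the half-width of a Visit 4 percentage grows by √(200/170) = 1.08, or about 8%. With 10 lost it grows by √(200/190) = 1.03, or about 3%. Precision barely suffers, so the effect on completion is the more visible one.

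**The case against.** The best defence is that the clause is a practical reminder and was never meant as an exclusion. Bringing the newborn makes little sense for a home visit, and the sentence that follows explains only why the swab needs face-to-face contact. Section 8.4 asks a woman who would withdraw over one procedure to continue with the rest. In a single-centre study, the team can be expected to know what was meant.

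This shows the likely intent, and it is why the point is minor. It does not change the wording, which is conditional. Section 8.4 concerns women who choose to withdraw. It does not reach a woman who is willing to be sampled but does not bring the baby.

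A reader might also infer more than the documents support:

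- **That every woman without a swab loses Visit 4.** The ward visit carries no such condition, and section 13.4.3 says completion does not need the swab.
- **That feedback is lost.** Section 10.3.4.1 allows both Visit 4 questionnaires by emailed link and the feedback form by post, and section 8.4 seeks feedback from women who withdraw. Section 11.2 describes Visit 4 as face to face, but that does not cancel the remote routes. They do not supply the maternal samples, however.
- **That mothers of preterm or sick babies are selectively lost.** Section 9.3.4 has a separate paragraph for premature delivery that does not mention bringing the newborn. A mother whose baby is still in hospital might also be seen in a clinical setting there. Selective loss is possible but not shown.
- **That women delivering during COVID-19 face a looser rule.** Section 10.6.5 is an emergency measure for women already enrolled. It is stricter in another respect: those who refuse or lack home freezing are withdrawn or wait to resume visits. Its relevance here is only that maternal sampling can proceed without the swab.

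**Conclusion.** The condition in section 9.3.4 conflicts with the optional status of the swab in sections 10.3.4.2 and 9.4 and with the completer definition in section 13.4.3. Followed as written, it leaves a limited group with no stated route to their own Visit 4 samples: women not seen on the ward who decline the swab or cannot bring the baby.

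The size is unknown from the documents. The assumed ranges give about 3 to 30 of 200 women, with 10 in the middle case. A claim that the effect exceeds the sampling error of the completion estimate is not supported across that range. It would also require the site to apply the sentence literally, which the documents neither confirm nor rule out.

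Severity is minor: a contradiction to be reconciled, confined to secondary endpoints.

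**What to change.** In section 9.3.4, remove the condition about bringing the newborn. State that the maternal Visit 4 procedures (self-samples, blood where consented, contact and feedback questionnaires) go ahead within the first postnatal week whether or not the newborn is swabbed. Record the swab separately as taken, declined or newborn not available, so that swab uptake can be reported apart from maternal completion.

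The cost is a sentence or two in the protocol and one field on the case report form, with no new study procedure. The one small downside is that swab uptake might fall slightly if the visit no longer depends on the baby being brought.
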